Boehringer
Ingelheim

Clinical Trial Protocol

Document Number:		c27319443-05
EudraCT No. EU Trial No.	2019-001673-93	
BI Trial No.	1368-0007	
BI Investigational Medicinal Product(s)	Spesolimab, (BI 655130)	
Title	An open label, long term safety trial of spesolimab treatment in patients with fistulising Crohn's disease who have completed previous spesolimab trials	
Lay Title	A study to test long-term treatment with spesolimab in patients with fistulising Crohn's disease who took part in previous trials.	
Clinical Phase	II	
Clinical Trial Leader	[REDACTED] Phone: [REDACTED] Fax: [REDACTED]	
Principal Investigator < or > Coordinating Investigator	[REDACTED]	
Status:	Final Protocol (Revised Protocol (based on global amendment No. 2))	
Version and Date	Version: 3.0	Date: 21 Jan 2021
Page 1 of 100		
Proprietary confidential information. © 2021 Boehringer Ingelheim International GmbH or one or more of its affiliated companies. All rights reserved. This document may not - in full or in part - be passed on, reproduced, published or otherwise used without prior written permission.		

CLINICAL TRIAL PROTOCOL SYNOPSIS

Company name	Boehringer Ingelheim
Protocol date	28 November 2019
Revision date	21 January 2021
BI trial number	1368-0007
Title of trial	An open label, long term safety trial of spesolimab treatment in patients with fistulising Crohn's disease who have completed previous spesolimab trials
Coordinating Investigator	
Trial site(s)	Multi-centre trial
Clinical phase	II
Trial rationale	Provide to patients with fistulising Crohn's disease extended acces to a potentially beneficial treatment and evaluate long term tolerability, safety, and efficacy.
Trial objective(s)	1. To evaluate the long-term safety of spesolimab in patients with fistulising Crohn's disease who have completed treatment in previous trials. 2. To evaluate the long-term efficacy of spesolimab in patients with fistulising Crohn's disease who have completed treatment in previous trials.
Trial endpoints	Primary Endpoint 
Exposure adjusted rate of patients with treatment emergent adverse event (AEs) up to week 336 Secondary Endpoints 
Proportion of patients with perianal fistula remission at weeks 48, 96, 144, 192, 240, 288, and 336Proportion of patients with perianal fistula response at weeks 48, 96, 144, 192, 240, 288, and 336
Trial design	Open label (OL), 7 year, single group, long-term extension study
Total number of treated patients	Up to 20
Number of patients on each treatment	All patients will receive spesolimab.
Diagnosis	Patients with fistulising Crohn's disease
Main in- and exclusion criteria	
Inclusion Criteria
 
Patient older than 18 years

	
Has completed all treatments as assigned and the EOT visit in the previous induction trial in fistulising CD and is willing and able to continue treatment in 1368-0007Has obtained an individual health benefit, per investigator judgement (such as fistula response or remission or other clinical improvement), from treatment in the parent trial.Signed and dated written informed consent for 1368-0007 in accordance with GCP and local legislation prior to admission into the trialWomen of childbearing potential (WOCBP) must be ready to use highly effective methods of birth control per ICH M3 (R2) 
Exclusion criteria
 
Have experienced study treatment-limiting adverse events during induction treatment with study drugHave developed any condition which meets the exclusion criteria from the original induction studyAny condition which in the opinion of the investigator affects the safety or ability to participate in this trial
Test product(s)	Spesolimab, BI 655130
dose	300 mg s.c./4 weeks 1200 mg i.v. followed by 600 mg s.c./4 weeks in case of fistula relapse
mode of administration	Subcutaneous (s.c.) Intravenous (IV) in case of fistula relapse
Comparator product(s)	Not applicable
dose	Not applicable
mode of administration	Not applicable
Duration of treatment	Approximately 7 years
Statistical methods	Descriptive statistics only.

FLOW CHART 1

FLOWCHART 1A: V1, M1-M13

Visit	V1 ¹	M1	M2	M3	M4	M5	M6	M7
Week	-2 to M1	1	4	8	12	16	20	24
Day	-14 to -7	1	29	57	85	113	141	169
Visit Window (days)	N.A	0	±7	±7	±7	±7	±7	±7
Visit type ²⁰	A	B	C	C	D	C	C	E
Informed Consent	X							
Eligibility criteria	X	X						
Demographics	X							
Medical/Surgical history	X							
eDiary		X	X		X			X
Rectoscopy or proctoscopy		X						
Physical exam (including vital signs), weight ³	X ^C	X ^T						
12 lead-ECG	X	X						
Pregnancy test ⁴	X	X	X	X	X	X	X	X
Concomitant therapy	X	X	X	X	X	X	X	X
Adverse events ¹¹	X	X	X	X	X	X	X	X
Pelvic MRI		X						
Safety laboratory test ⁰	X	X			X			X
QuantiFERON-TB test	X							
Blood infection testing	X							
		X	X					
		X	X					
		X	X					
Stool sampling for enteric pathogens ¹³	X							
Urine sampling for albumin	X							
		X	X					
		X	X					
Contact IRT	X	X	X	X	X	X	X	X
Study drug administration ¹¹		X	X	X	X	X	X	X
Local tolerability assessment		X	X	X	X	X	X	X

Visit	M8	M9	M10	M11	M12	M13
Week	28	32	36	40	44	48
Day	197	225	253	281	309	337
Visit Window (days)	±7	±7	±7	±7	±7	±7
Visit type ²⁰	C	C	D	C	C	F
Informed Consent						
Eligibility criteria						
Demographics						
Medical/Surgical history						
eDiary			■		■	
Rectoscopy or proctoscopy					■	
Physical exam (including vital signs), weight ³	X ^T	X ^C				
12 lead-ECG						X
Pregnancy test ⁴	X	X	X	X	X	X
Concomitant therapy	X	X	X	X	X	X
Adverse events ^{1/}	X	X	X	X	X	X
Safety laboratory test ⁶				X		X
QuantiFERON-TB test						X
Contact IRT	X	X	X	X	X	X
Study drug administration	X	X	X	X	X	X
Local tolerability assessment	X	X	X	X	X	X

Continue with M14 to M84 according visit type and
then to end of treatment and end of study visits.

FLOWCHART 1B: M14-M84

See [flow chart 1A](#) for procedures to be done depending on visit type. The same visit schedule repeats yearly until the end of seven years as follows.

These treatment visits will follow the same ± 7 day visit window.

M14-M25												
Visit	M14	M15	M16	M17	M18	M19	M20	M21	M22	M23	M24	M25
Week	52	56	60	64	68	72	76	80	84	88	92	96
Day	365	393	421	449	477	505	533	561	589	617	645	673
Visit type	C	C	D	C	C	E	C	C	D	C	C	F [#]
M26-M37												
Visit	M26	M27	M28	M29	M30	M31	M32	M33	M34	M35	M36	M37
Week	100	104	108	112	116	120	124	128	132	136	140	144
Day	701	729	757	785	813	841	869	897	925	953	981	1009
Visit type	C	C	D	C	C	E	C	C	D	C	C	F*
M38-M49												
Visit	M38	M39	M40	M41	M42	M43	M44	M45	M46	M47	M48	M49
Week	148	152	156	160	164	168	172	176	180	184	188	192
Day	1037	1065	1093	1121	1149	1177	1205	1233	1261	1289	1317	1345
Visit type	C	C	D	C	C	E	C	C	D	C	C	F*
M50-M61												
Visit	M50	M51	M52	M53	M54	M55	M56	M57	M58	M59	M60	M61
Week	196	200	204	208	212	216	220	224	228	232	236	240
Day	1373	1401	1429	1457	1485	1513	1541	1569	1597	1625	1653	1681
Visit type	C	C	D	C	C	E	C	C	D	C	C	F*
M62-M73												
Visit	M62	M63	M64	M65	M66	M67	M68	M69	M70	M71	M72	M73
Week	244	248	252	256	260	264	268	272	276	280	284	288
Day	1709	1737	1765	1793	1821	1849	1877	1905	1933	1961	1989	2017
Visit type	C	C	D	C	C	E	C	C	D	C	C	F*
M74-M84												
Visit	M74	M75	M76	M77	M78	M79	M80	M81	M82	M83	M84	
Week	292	296	300	304	308	312	316	320	324	328	332	
Day	2045	2073	2101	2129	2157	2185	2213	2241	2269	2297	2325	
Visit type	C	C	D	C	C	E	C	C	D	C	C	

*Visit type F after visit M25: no blood and stool sampling for biomarkers

FLOWCHART 1C: END OF TREATMENT AND END OF STUDY VISITS

Trial Periods	M85/EOT	EOS¹²
Visit		
Week	336	352
Day	2353	2466
Visit Window (days)	+7	+7
eDiary		
Rectoscopy or proctoscopy		
Physical exam (including vital signs),weight ³	X ^c	X ^c
12 lead-ECG	X	X
Pregnancy test ⁴	X	X
Concomitant therapy	X	X
Adverse events ^{17, 19}	X	X
Safety laboratory test ⁶	X	X
QuantiFERON-TB test	X	X
Blood infection testing ²¹	X	
Study drug administration ¹²	X	
Contact IRT	X	
Local tolerability assessment	X	
Study completion		X

FLOW CHART 2A: PATIENTS WITH INFLAMMATORY FLARE WITH NO FISTULA RELAPSE

These visits will be done when the patient presents with a flare but no fistula relapse starting with flare confirmation visit, followed with visits F1 to F6, re-start at F1 and repeat visits type F1 to F6 until EOT or a new flare or fistula relapse occurs.

Naming convention will be i.e.: FL02V04F5: second flare, flare visit number 4, visit type 5
 Flare Confirmation number: FLn (luminal flare and fistula relapse will count as consecutive numbers)

Visit number: Vn (consecutive number of visits at each flare/relapse)

Visit type: from F1 to F6

Trial periods	Flare confirmation	Flare maintenance treatments					
		F1n	F1	F2	F3	F4	F5
Visit							
FLn							
Week (always count after last dose of of maintenance treatment) ²²	N.A.	4	8	12	16	20	24
Day ²²	N.A.	29	57	85	113	141	169
Visit Window (days)	N.A.	±7	±7	±7	±7	±7	±7
eDiary		█	█	█	█	█	
		█	█	█	█	█	█
Ileocolonoscopy+ [REDACTED], [REDACTED]	X			X			
Physical exam (with vital signs), weight ³	X ^T	X ^T	X ^T	X ^T	X ^T	X ^T	X ^T
12-lead ECG	X			X			X
Pregnancy test ⁴		X	X	X	X	X	X
Concomitant therapy	X	X	X	X	X	X	X
Adverse events ¹⁷	X	X	X	X	X	X	X
Safety laboratory tests ⁶	X	X		X		X	
	█						█
	█			█			█
	█			█			█
Stool sampling for enteric pathogens ¹⁵	X						
	█						█
Contact IRT	X	X	X	X	X	X	X
Study drug administration ²²		X	X	X	X	X	X
Local tolerability assessment		X	X	X	X	X	X

FLOW CHART 2B: FISTULA RELAPSE (WITH OR WITHOUT A LUMINAL FLARE)

These visits will be done when the patient presents with a fistula relapse, with or without luminal flare, starting with fistula relapse confirmation visit, followed by an IV reinduction visit and then visits F1 to F6, re-start at F1 and repeat visits type F1 to F6 until EOT or a new fistula relapse occurs.

Naming convention will be i.e.: FL02V04F5: second fistula, fistula visit number 4, visit type 5

Fistula relapse confirmation number: FLn (luminal flare and fistula relapse will count as consecutive numbers)

Visit number: Vn (consecutive number of visits at each flare/fistula relapse)

Visit type: from F1 to F6

Trial periods	Fistula confirmation	i.v. reinduction	Flare/Fistula relapse maintenance treatments					
			F1	F2	F3	F4	F5	F6
Visit	FLn	Rn						
Week	0	0	4	8	12	16	20	24
Day	-5 to -3	0	29	57	85	113	141	169
Visit Window (days)	N.A.	±2	±7	±7	±7	±7	±7	±7
eDiary								
Seton placement if needed (should be retired after 4wk)	X							
Eligibility criteria		X						
Physical exam (with vital signs), weight ³	X ^T	X ^T	X ^T	X ^T	X ^T	X ^T	X ^T	X ^T
Rectoscopy, proctoscopy ²			Every 48 weeks, done with MRI					
12-lead ECG		X			X			X
Pregnancy test ⁴		X	X	X	X	X	X	X
Concomitant therapy	X	X	X	X	X	X	X	X
Adverse events ¹⁷	X	X	X	X	X	X	X	X
Safety laboratory tests ⁶	X		X		X		X	
Contact IRT		X	X	X	X	X	X	X
Study drug administration ¹⁴		X	X	X	X	X	X	X
Local tolerability assessment			X	X	X	X	X	X

FLOW CHART 2C: PATIENTS WITH FLARE/FISTULA RELAPSE –EOT/EOS VISIT

Trial periods	Follow-up	
	EOT	EOS ¹²
Visit		
Week	336 wk from initial MI	16 wk after EOT
Day	2353 days after initial MI	113 days after EOT
Visit Window (days)	±7	+7
eDiary		
Ileocolonoscopy, rectoscopy, proctoscopy	X ¹³	
Physical exam (with vital signs), weight ³	x ^c	x ^c
12-lead ECG		
Pregnancy test ⁴	X	X
Concomitant therapy	X	X
Adverse events ^{17,19}	X	X
Safety laboratory tests ⁶	X	X
Blood Infection testing ²¹	X	
Contact IRT	X	
Study drug administration ¹²	X	
QuantiFERON-TB test ¹⁸	X	X
Local tolerability assessment	X	
Study completion		X

Footnotes

1. Visit V1 of this long-term extension study should be performed preferably during the last visit (EOT) of the preceding trial. This is strongly recommended. In case it is not possible at EOT visit, maximum days allowed between trials from EOT parent trial to V1 of this trial will be 28 days. Procedures of V1 will not need to be repeated if patient do not have any clinical significant change.
2. Rectoscopy or proctoscopy have to be performed every 48 weeks during maintenance treatment period. Additional it has to be done: a) at screening (EOT of parent trial); full ileocolonoscopy/colonoscopy/sigmoidoscopy, instead of proctoscopy or rectoscopy could be performed if clinically indicated as per investigator judgement b) In case of inflammatory flare, an unscheduled confirmatory ileocolonoscopy has to be performed. An ileocolonoscopy after 12 weeks to check response to flare treatment is not mandatory but could be performed if clinically indicated as per investigator judgement
3. Physical examination: C=complete, T=targeted. Refer to [Section 5.2.1](#) and [5.2.2](#). Measurement of vital signs should precede blood sampling and be assessed pre-dose at all dosing visits and at screening for visit F1 in case of inflammatory fistula relapse, with i.v. study drug administration, vital signs will be assessed at approximately 5 and 60 minutes after study drug administration. Monitor for signs and symptoms of hypersensitivity reactions for 1h following i.v. study drug administration. At s.c. dosing visits, vital signs will be assessed at approximately 10 minutes after study drug administration. Also at Visit M1 and Visit M2 (s.c. dosing visits) additional vital signs assessments will be performed approximately 60 minutes post-dose (i.e. 60 min. after last injection).
4. For women of childbearing potential. Urine pregnancy tests will be performed at all visits indicated in the [Flow Chart](#). In case of a positive urine pregnancy test, a serum pregnancy test will be done. Urine pregnancy testing should be done at screening and later prior to administration of study drug. Study drug should only be administered in case of a negative test result. More frequent testing should be done if required by the local regulation or per investigator judgment.
5. [REDACTED]
6. Includes clinical chemistry, hematology, coagulation and urinalysis assessments. Patient is not required to be fasting prior to blood collection. If fasted mark it on laboratory requisition form. At visits with study drug administration scheduled blood sampling should be done prior to the study drug administration. TSH and Glycosylated Hbc (HbA1c) tests have to be done at screening and then every 48 weeks at visit type F. See [section 5.2.3](#) safety laboratory parameters for complete list of testing required.
7. [REDACTED]
8. [REDACTED]
9. [REDACTED]
10. [REDACTED]
11. First study drug will be administered at M1.
12. For patients who discontinue study medication before scheduled end of treatment, an early EOT visit has to be scheduled. No treatment administration will be done at this visit. EOS visit will be 16 weeks after last dose of study medication.
13. For patients with inflammatory flares only, endoscopy (rectoscopy, proctoscopy, sigmoidoscopy, colonoscopy or full ileocolonoscopy) does not need to be repeated if done within 6 weeks prior to EOT visit.
14. Patients who develop a fistula relapse will receive a single infusion of 1200mg spesolimab i.v. followed 4 weeks later by intensified maintenance treatment with 600mg spesolimab s.c. q4W until the originally scheduled EOT visit (i.e. at week 336 after start of first sc. maintenance treatment)
15. Stool sampling for enteric pathogens only need at visit 1 and in case of inflammatory flare, according routine medical practice. If collection is not possible at visit 1, stool sample has to be collected at visit M1.
16. [REDACTED]
17. Please see [Section 5.2.6.2.1](#) for important instructions regarding AE collection in parent and extension trial further below
18. Quantiferon in all patients, either in maintenance [flowchart](#) or in case of flare/fistula relapse), will be tested every 48 weeks (aprox 1 year) from day 1 (visit M1), and at EOT and EOS.
19. After the EOS visit (individual patient's end of the trial) the investigator should report only any cancers of new histology and exacerbations of existing cancer (if applicable), trial treatment related SAEs and trial treatment related AESIs of which the investigator may become aware of and only via the BI SAE form for this extension trial , please see [section 5.2.6.2.1](#).
20. Visit types include all procedures that should be done at every type of visit from week 48(M13), see [flow chart 1B](#).
21. Infection testing for HBV (not HCV and HIV) to be repeated at EOT
22. Patients who present a luminal inflammatory flare (but NO fistula relapse) might receive standard of care treatment for flare as per investigator judgement, while continuing with their spesolimab maintenance dose of 300mg s.c. visit F1 will be done 4 weeks after last visit dosed, but not after flare confirmation visit.

TABLE OF CONTENTS

TITLE PAGE	1
CLINICAL TRIAL PROTOCOL SYNOPSIS	2
FLOW CHART 1.....	4
FLOWCHART 1A: V1, M1-M13	4
FLOWCHART 1B: M14-M84	6
FLOWCHART 1C: END OF TREATMENT AND END OF STUDY VISITS	7

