Based on the strong rationale ([section 1.3](#)), there is a reasonable chance that spesolimab may promote healing in fistulising CD. Moreover only patients deriving an individual health benefit from spesolimab in the parent study (e.g. by achieving a fistula response or remission or other clinical improvement), will be offered to roll-over into this study and directly receive open label active spesolimab maintenance treatment (300mg s.c. q4w) for up to 7 years. Patients experiencing a fistula relapse in this long-term study will be offered to receive high dose treatment (1200mg IV single dose) followed by an intensified spesolimab maintenance treatment (600mg s.c. q4W). Patients who present a luminal inflammatory flare without fistula relapse might receive antiinflammatory therapy as per SOC to treat luminal flare based on clinician judgement while continuing the same spesolimab maintenance dose (300 or 600 mg s.c. q4w).

Patients who present a fistula relapse with negative spesolimab drug level (with or without ADA) or who experience fistula relapse more than twice within a 12 month time period will be discontinued and switched to available SOC at the investigator's discretion. This will allow patients to receive an initial high dose spesolimab re-treatment, whilst limiting the duration of spesolimab exposure in patients no longer benefitting from treatment.

Therefore, based on the eligibility criteria and the safety profile as currently known (see [section 1.2](#)), all patients participating in this trial are expected to receive clinical benefit with acceptable risks. Participation in this study may thus help to maintain individual benefit and to generate future benefit for larger groups of patients with CD if spesolimab proves to be successful in treating this disease.

In order to protect the patient's safety during conduct of this trial, an independent Data Monitoring Committee has been established for the periodic review of clinical trial safety data

Table 1.4:1 Further IMP or trial related risks and mitigation measures

Hypothetical risks of clinical relevance for this trial	Summary of data, rationale for the risk	Mitigation strategy

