Fistula relapse is suspected if ≥ 1 external fistula orifice re-emerges, which was open at baseline or newly emerged during the preceding trial but was closed at completion of the parent study or at any time during the current trial; or which emerged newly. Fistula relapse is confirmed in a second independent visit ([Flowchart 2B](#)).

A patient with a confirmed fistula relapse will receive a single i.v. infusion of 1200mg spesolimab. At week 4 after the single i.v. infusion dose, patients will continue with an intensified subcutaneous spesolimab maintenance dosing of 600mg q4W, as seen in [Figure 3.1:2](#). An additional visit has to be planned at week 12 after the single i.v. infusion to check the patient's response status. For patients with fistula relapse, this week 12 assessment will include clinical assessment, [REDACTED] and MRI, which will guide investigator judgment of patient response status.

Luminal inflammatory flare, is defined as an increase in PRO-2 score [sum of 7-day weighted stool frequency (SF) and abdominal pain (AP) , components of the [REDACTED], using the original [REDACTED] multiplying factors of 2 for SF and 5 for AP] by >50 points from baseline of the current trial, plus an increase in [REDACTED] score by ≥ 100 points from baseline of the current trial with an absolute [REDACTED] >220 in a second independent confirmation visit, with an absolute [REDACTED], in absence of enteric pathogens in stool. In case of a suspected inflammatory flare, the site will ask the patient to immediately start entering his [REDACTED] symptom score data into the eDiary until the next scheduled or unscheduled visit at which a flare confirmation assessment will be performed, and then to continue entering the data as planned (i.e. for 10 days before each visit).

A patient with a luminal inflammatory flare (endoscopically confirmed) without fistula relapse might be treated as per SOC based on clinician judgement while continuing the same spesolimab maintenance dose according [flow chart 2A](#). After 12 weeks of flare confirmation (visit F3) a new rectoscopy/proctoscopy and [REDACTED] assessment will be performed to assess luminal flare response to SOC as per investigator judgement. For details of trial procedures, please follow the [Flow chart 2A](#).

Figure 3.1:2 Trial design in case of fistula relapse

[figure not shown]

Figure 3.1:3 Trial design in case of luminal inflammatory flare

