The administration of the trial medication intravenously on all applicable study days will be done under supervision of the investigating physician or a designee at the site. If available, a pharmacist should prepare the study medication. The four eye principle (two-person rule) should be applied for preparation (e.g. choosing the correct vials with the correct medication number) and administration of trial medication.

Dose modifications or adjustments are not permitted. In exceptional cases of missed or delayed visits, if any of these visits has to be rescheduled, the date of subsequent visit should be calculated from Day 1 of maintenance treatment or if the patient is on fistula relapse treatment from the first s.c. drug administration after the last fistula relapse. There should be at least 14 days between two consecutive study drug administrations.

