4.2 OTHER TREATMENTS, EMERGENCY PROCEDURES, RESTRICTIONS

4.2.1 Other treatments and emergency procedures

4.2.1.1 Allowed concomitant therapies

CD-Related Treatments

Patients in this trial may be on conventional immunosuppressants or anti-TNF α biologic treatment for CD. These may consist of one or more of the following drugs (cf. [Section 4.2.1.2](#)

for restrictions), which are therefore permitted concomitant medications:

- Oral 5-ASA compounds, provided that dose has been stable prior to randomisation in parent trial and during current trial, and/or
- Oral corticosteroids (≤ 20 mg per day of prednisone or equivalent), provided that dose has been stable prior to randomisation in parent trial and during current trial, and/or
- Oral budesonide (≤ 9 mg per day), provided that dose has been stable in parent trial and during current trial, and/or
- Azathioprine, 6-MP, 6-TG or methotrexate, provided that dose has been stable in parent trial and during current trial,
- Approved anti-TNF α (e.g. infliximab, adalimumab, certolizumab pegol; or respective biosimilars) provided that dose has been stable in parent trial and during current trial
- Probiotics (e.g. *S. boulardii*) provided that dose has been stable for > 4 weeks prior to randomisation
- Regular use of anti-diarrheals

Dose has to be stable before rolling over and throughout the trial. The only exceptions are anti-diarrheals, which may be adjusted to current symptoms, and steroid reduction.

Patients who present a luminal flare (but no fistula relapse) might receive standard of care treatment for moderate-to-severe CD, while continuing with their spesolimab maintenance dose. Thus, on top of the concomitant therapies listed above, patients with luminal flare (but no fistula relapse) are also allowed to receive concomitant approved doses for treatment of moderate to severe CD including (but not limited to) the following therapies:

- anti-TNF α (this might be associated to Azathioprine / 6-MP/ MTX)
- Integrin receptor antagonists
- IL12/ 23 antagonists

Steroids

Systemic steroids dosed intravenously or orally for less than 24 hours as treatment of infusion or anaphylactic reactions are permitted and do not lead to treatment discontinuation (see [Table 4.2.1.2:1](#)).

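### Footnote 22 gives only 300 mg as the maintenance dose during a luminal flare, which is wrong for a patient already raised to 600 mg after a fistula relapse

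*Protocol*

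**What the plan says.** Several places in the Protocol set the spesolimab dose for a patient with a luminal flare but no fistula relapse.

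- **Footnote 22** (on the week, day and study drug rows of Flow Chart 2A): standard care for the flare is allowed "while continuing with their spesolimab maintenance dose of 300mg s.c". No 600 mg option appears, and patients intensified earlier are not excluded.
- **Section 1.4**: the patient may be treated for the flare "while continuing the same spesolimab maintenance dose (300 or 600 mg s.c. q4w").
- **Section 3.1**: standard care "while continuing the same spesolimab maintenance dose according" Flow Chart 2A, with no figure in mg.
- **Section 4.2.1.1**: such patients "might receive standard of care treatment for moderate-to-severe CD, while continuing with their spesolimab maintenance dose", again with no figure.
- **Section 4.1.4**: "Dose modifications or adjustments are not permitted".

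For patients who have had a fistula relapse, **footnote 14** (on the study drug row of Flow Chart 2B) prescribes one 1200 mg infusion, "followed 4 weeks later by intensified maintenance treatment with 600mg spesolimab s.c. q4W until the originally scheduled EOT visit".

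**The concern.** A patient can have a fistula relapse, go up to 600 mg every 4 weeks, and later have a luminal flare without a new relapse. Section 1.4 foresees this patient, because it names 600 mg as a possible dose during a luminal flare. The flow charts also number flares and relapses in one consecutive series per patient. For this patient footnote 22 states a dose that disagrees with Section 1.4 and footnote 14.

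Footnotes to the visit schedule are what a site is likely to consult at a dosing visit. Following the 300 mg figure would halve the dose. Section 4.1.2 explains that 600 mg is meant to give twice the exposure of the regimen on which the patient relapsed, so the literal figure would put the patient back on that regimen.

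**Working it through.** There is no plan figure to reproduce. The check is a comparison of the dosing statements for the two kinds of patient who can have a luminal flare without a fistula relapse.

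| Source | Patient on 300 mg q4w | Patient on 600 mg q4w after an earlier relapse |
|---|---|---|
| Footnote 22 | 300 mg | 300 mg if read literally |
| Section 1.4 | same dose: 300 mg | same dose: 600 mg |
| Footnote 14 | not applicable | 600 mg until scheduled end of treatment |
| Section 3.1 | same dose | same dose |
| Section 4.2.1.1 | own maintenance dose | own maintenance dose |
| Section 4.1.4 | no dose change | no dose change |

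The first column agrees throughout. In the second, only footnote 22 gives 300 mg. Its sentence is nearly the one in Section 4.2.1.1 with a figure added, and the figure creates the mismatch.

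**Size per visit.** Table 4.1.1:1 gives 150 mg per 1 mL syringe.

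- 300 mg: 300 / 150 = 2 injections.
- 600 mg: 600 / 150 = 4 injections.
- Ratio: 300 / 600 = 0.5 of the intended dose.

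The injection counts apply to the 1 mL syringe only. For the 2 mL device the table gives one injection for either dose. The ratio in mg does not depend on the device.

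**Number of patients.** Neither document says how many patients had a fistula relapse followed by a luminal-only flare. With up to 20 patients planned (Section 7.5), the range is 0 to 20. The upper end would need every patient to follow that sequence, and Section 3.1 allows later entry from other spesolimab trials, so 20 is a planning figure and not a firm ceiling. No cumulative dose shortfall is projected, because neither the patients nor the doses affected are known.

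**Which flow chart applies.** The introduction to Flow Chart 2A reads "These visits will be done when the patient presents with a flare but no fistula relapse starting with flare confirmation visit", with no exception for a patient who relapsed earlier, and Section 3.1 sends this flare to 2A. The introduction to 2B has patients "re-start at F1 and repeat visits type F1 to F6 until EOT or a new fistula relapse occurs", which can be read as keeping an intensified patient on 2B. As shown, only 2A of these two charts has a row for the ileocolonoscopy that footnote 2 requires to confirm a flare. A site could therefore reasonably use 2A and meet footnote 22. Figure 3.1:3, which might settle this, is not shown in the copy reviewed.

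**The case against.** The strongest reply is that an intensified patient never leaves Flow Chart 2B. The 2A cycle stops at end of treatment, a new flare or a fistula relapse. The 2B cycle stops only at end of treatment or a new fistula relapse. 2B is titled as covering relapse with or without a luminal flare, and its dosing columns are headed for both. On that reading footnote 22 addresses only patients still on 300 mg, and Section 1.4 names both doses because it spans both pathways. This is a possible reading, but the text does not settle it, and Section 3.1 and the 2A introduction point the other way.

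The second reply is that the dose is clear anyway. Footnote 22 speaks of continuing the patient's own dose, Sections 1.4, 3.1 and 4.2.1.1 agree, Section 4.1.4 bars adjustments, and treatment is assigned through the interactive response system. This stands as to intent: footnote 22 does not order a reduction. It does not make the figure right, and the documents do not say how the system handles this case.

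The third reply is that the correction has little practical value. The SAP describes the final analysis of a discontinued trial, so few if any future doses are at stake. Section 7.2.1 already lets the study team classify any violation it considers important, and SAP Section 7.7 tabulates s.c. and i.v. exposure in mg. This stands too, and it is why the point is minor.

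**Conclusion.** The inconsistency is real and lies in current text. Footnote 22 names a single dose where Section 1.4 names two, and for a patient already on 600 mg its figure is half the dose that Section 1.4 and footnote 14 require. Footnote 22 is the outlier.

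Severity is minor. A practical consequence requires that a patient had a fistula relapse and then a luminal-only flare, that the site used Flow Chart 2A, and that the 300 mg figure was followed despite the other sections and the interactive response system. None of this is shown to have happened, and the number of patients concerned may be zero. No sample size, error rate or planned analysis is affected. Confidence is high that the wording is inconsistent; whether any dose was wrong cannot be judged from the documents.

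**What to change.** In footnote 22, replace the fixed figure so that the patient continues the *current spesolimab maintenance dose (300 mg, or 600 mg if previously intensified, s.c. q4w)*. This matches Section 1.4 and footnote 14 whichever flow chart the site uses.

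Because the trial is closing, a useful optional step is one more item in the protocol-violation review that Section 7.2.1 provides for before database lock: did any patient on 600 mg every 4 weeks receive 300 mg after a luminal flare? SAP Section 7.3 drops treatment compliance reporting, so a halved dose would not show there. The exposure data in mg that SAP Section 7.7 already requires should help to answer the question.

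The cost is one phrase in a footnote and, if the check is done, one review item for up to 20 planned patients. No analysis changes.
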